Exclusion Criteria	
 • Current or history of cardiovascular, pulmonary, neurological, endocrine, or renal disease that would preclude the involvement in the study. • TENS use in the last 5 years • Pacemaker • Uncontrolled blood pressure or diabetes • Neuropathic pain condition • Systemic autoimmune disorder (Lupus, PMR, RA, Psoriatic arthritis) • Spinal fusion – cervical or lumbar • Metal implants in the spine • Severe skin allergy to adhesive • Allergy to nickel • Pain less than 4 • Pregnancy • Epilepsy • Change in or new drug or treatment program within the last month or in the next 2months, i.e. must have a stable treatment plan • Unstable medical or psychiatric condition which in the opinion of the investigator could compromise the subject’s welfare or confound the study results
Planned Sample Size	Final sample size of 264 subjects divided into 88 subjects per group. We will recruit 316 subjects based on a 20% projected attrition.
Randomization	Patients will be randomly allocated on the second visit after a re-assessment of eligibility. We will use a permuted block schedule, stratified by site. The randomization schedule will be implemented using SAS v9.2 PROC PLAN, creating blocks of size 6 for each of the strata factors.
Study Device Dosage and Administration	
FDA Summary of Empi Select TENS Unit: TENS is a non-pharmacological agent which delivers electrical stimulation by a battery operated device via electrodes placed on the skin. TENS is considered to be a safe, inexpensive and non-invasive modality used to treat a variety of acute and chronic pain conditions.
 
510(k) Summary for 300 PV Complete Electrotherapy Systems 1. Manufacturer Empi [name]

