
Statistical Methods Aim #1- #4
	
Aim #1: The primary endpoint of Aim #1 is the change (visit 3- visit 2) in pain scores during movement. In order to evaluate the effectiveness of long-term use of TENS (Aim 1), the primary analysis will be the comparison of change in pain (with movement for those randomized to either active TENS, placebo TENS, or standard of care). The comparison of the change (visit 3 – visit 2) in pain for the three groups will be made using linear mixed model analysis for repeated measures with treatment group, time (visit2 and visit3), and treatment group*time interaction as the fixed effects. The test for the treatment group*time interaction effect corresponds to the test comparing mean change among the groups. Post-hoc pairwise comparison of mean change between groups will performed by test of mean contrasts estimated from the fitted linear mixed model with p-values adjusted using Bonferonni’s method to account for the number of tests performed (i.e. 3 tests for all pairwise comparisons). It is expected that the randomization will lessen the need for covariate-adjusted analyses. However, in the event that adjusted analyses are necessary, a secondary comparison of the change in endpoints for the three groups will be made by expanding the linear mixed model to include covariates. Potential confounders include age, race, ethnicity, educational attainment, marital status, TENS dose/intensity, change in opioid status, medication intake and use of rescue medications.
 
While every effort will be made to follow-up with patients, preliminary data suggests that approximately 10% of the patients will not return for follow-up. The ITT analysis will be performed using all available data for all randomized participants. In the presence of missing data, under the assumption of missing at random (MAR), linear mixed model analysis which can handle incompletely observed subjects and uses a likelihood estimation method will provide correct likelihoods and lead to valid estimates (ref1). However, since the data under analysis cannot distinguish if data is MAR or it is missing not at random (MNAR), sensitivity analysis will also be performed using pattern mixture models. Multiple imputations will be used for sensitivity analysis by imputing from a non-random pattern mixture model (ref2).
 
Furthermore, based on previous work, it is expected that approximately 5% of subjects randomized to active TENS may not receive a full dose of active TENS because they did not achieve the adequate intensity dose. In the primary ITT analysis, these patients will be included as randomized. However, as an additional analysis a modified ITT (mITT) analysis will be conducted. This analysis will utilize an ITT principle in terms of randomization but will be limited to those who achieved at least one adequate intensity dose.
 
(ref1) Molenberghs G. and Kenward MG (2007) Missing Data in Clinical Studies. John Wiley & Sons Ltd, West Sussex, England.

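### The primary Aim #1 test compares raw V3−V2 change and uses neither V2 movement pain nor site; if V2 is a true baseline, this costs roughly 0–35% in variance under plausible assumptions

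*Combined protocol and SAP*

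**What the plan says.** The Study Synopsis (Statistical Methods Aim #1–#4, Aim #1) takes change in movement pain from visit 2 to visit 3 as the primary endpoint and analyses it by "linear mixed model analysis for repeated measures with treatment group, time (visit2 and visit3), and treatment group*time interaction as the fixed effects". It then states: "The test for the treatment group*time interaction effect corresponds to the test comparing mean change among the groups". Pairwise contrasts are Bonferroni-adjusted for three tests. No covariance structure is given.

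Covariate adjustment is secondary and only if judged necessary. The Synopsis list reads: "Potential confounders include age, race, ethnicity, educational attainment, marital status, TENS dose/intensity, change in opioid status, medication intake and use of rescue medications". The Data Analysis Plan table repeats this list with BMI added. Neither list names V2 movement pain or site.

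On design, the Randomization row says "We will use a permuted block schedule, stratified by site", and on timing, "Patients will be randomly allocated on the second visit after a re-assessment of eligibility". It does not say when during that visit the allocation is disclosed.

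In the Order of Testing table, Session 2 lists the eligibility check, then a 6MWT with no rating label, then TENS, then a second 6MWT. Only the second carries the movement-pain, fatigue and Borg label.

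**The concern.** Randomisation makes the arms equal in expected V2 pain, provided V2 is measured before treatment. The planned model does not use that fact. It estimates a separate V2 mean for each arm and subtracts it in full, so chance imbalance at V2 enters the contrast with a weight of one instead of the regression weight. Each pairwise test runs at 0.05/3 = 0.0167, so the lost precision matters. The Aim #2 comparisons between randomised groups follow the Aim #1 method and inherit the same loss.

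The second issue is whether V2 is a baseline at all. If its only movement-pain score is taken with TENS running, the V2 means would be expected to differ by arm, because the Study Rationale reports that a single active treatment lowered movement pain relative to placebo. Adjusting for V2 would then be wrong, and raw V3−V2 change would not be a clean one-month effect either.

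**Working it through.** **Inputs.** From the documents: 88 per arm in three arms; 0.0167 per pairwise test; loss to follow-up from "preliminary data suggests that approximately 10% of the patients will not return for follow-up" and, in the Planned Sample Size row, "We will recruit 316 subjects based on a 20% projected attrition". The 88 per arm cannot be reproduced, because no effect size, SD, power or correlation is stated.

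Assumed: ρ, the V2–V3 correlation, at 0.3 to 0.9; and k = SD(V2)/SD(V3), at 1, 0.85 and 0.7. Values of k below 1 represent the possibility that the exclusion "Pain less than 4" narrows the V2 distribution. The NRS ICC of 0.71–0.99 in Table 1 is a reliability, not a one-month correlation under treatment.

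**Variance.** In units of SD(V3)²/n per arm, with f the fraction having V3:

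- adjusted (ANCOVA, or constrained model with unstructured covariance): (1 − ρ²)/f
- planned: (1 − ρ²)/f + (k − ρ)²

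The planned variance is never the smaller of the two, and they are equal only when k = ρ. Example with k = 1, ρ = 0.5, f = 1: 0.75/(0.75 + 0.25) = 0.75.

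Ratio of adjusted to planned variance:

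| k | f | ρ=0.3 | ρ=0.5 | ρ=0.7 | ρ=0.9 |
|---|---|---|---|---|---|
| 1 | 1 | 0.65 | 0.75 | 0.85 | 0.95 |
| 1 | 0.9 | 0.67 | 0.77 | 0.86 | 0.95 |
| 1 | 0.8 | 0.70 | 0.79 | 0.88 | 0.96 |
| 0.85 | 1 | 0.75 | 0.86 | 0.96 | 0.99 |
| 0.85 | 0.9 | 0.77 | 0.87 | 0.96 | 0.99 |
| 0.85 | 0.8 | 0.79 | 0.88 | 0.97 | 0.99 |
| 0.7 | 1 | 0.85 | 0.95 | 1.00 | 0.83 |
| 0.7 | 0.9 | 0.86 | 0.95 | 1.00 | 0.84 |
| 0.7 | 0.8 | 0.88 | 0.96 | 1.00 | 0.86 |

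A simulation with three arms of 88, k = 1 and complete data gave savings of 32%, 24%, 16% and 4% across the four values of ρ, against 35%, 25%, 15% and 5% by formula.

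**Sample size and power.** At k = 1 with complete data, the adjusted analysis matches 88 per arm on raw change with 88(1 + ρ)/2 = 57, 66, 75 or 84 per arm. If raw change had 80% power at 0.0167 (assumed), adjusted power is Φ(3.236/√ratio − 2.394):

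- k = 1: 95, 91, 87, 82%
- k = 0.85: 91, 86, 82, 81%
- k = 0.7: 87, 82, 80, 88%

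**Site.** A constant site effect cancels from change. If the sites differ in mean change by δ SD and are of equal size, omitting site makes the SE too large by √(1 + δ²/4): 1.005 at δ = 0.2 and 1.031 at δ = 0.5.

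**Covariance in the remedy.** A constrained model fitted with compound symmetry uses slope b = 2ρk/(1 + k²). Its true variance is 1 − b², but it reports (1 + k²)/2 × (1 − b²). The reported SE is therefore √((1 + k²)/2) of the true one: 0.928 at k = 0.85 and 0.863 at k = 0.7. Type I error becomes about 0.026 and 0.039 against 0.0167. At k = ρ = 0.7 its variance is also 1.11 times that of raw change.

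**If V2 is scored with TENS on.** Let d be the single-session effect at V2 and D the effect at V3. Raw change estimates D − d, and the adjusted contrast estimates D − (ρ/k)d, for example D − 0.59d at k = 0.85, ρ = 0.5. Neither equals D unless d = 0. The documents do not give d on the NRS.

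**The case against.** The plan is internally consistent: endpoint, model and stated interpretation agree, and the contrast is valid under randomisation. Preferring baseline adjustment improves efficiency; it does not correct an error. That stands, and the point is put as one about precision.

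The size is assumed, and its range includes zero. Using the ICC of 0.71–0.99 as a rough ρ with equal SDs gives a saving of only 0.5–14.5%. Nor is 35% a ceiling: ρ = 0.3 with k = 1.2 gives 47%. The pain exclusion is not said to concern movement pain, so k = 0.7 is speculative. All of this stands.

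On complete data, the covariance structure does not affect the planned unconstrained contrast, so the compound-symmetry figures say nothing against the plan. That is also right: they are a caution about how the remedy is fitted.

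The V2 timing doubt rests on a table label that may be shorthand, since the first walk is unlabelled at Sessions 3 and 4 too, and Table 1 lists movement NRS at every visit. That weakens any inference that no pre-TENS score exists, but nothing else in the documents shows that one does.

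Finally, the covariate list is open-ended and could admit V2 pain or site. But that route is secondary and conditional, so it leaves the primary test unchanged.

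**Conclusion.** The point holds as a recommended improvement, with medium confidence. Given a V2 movement-pain score taken before allocation is disclosed and before TENS starts, the planned test is unbiased (under MAR if V3 is missing) but imprecise. Adjusting for V2 would cut the contrast variance by roughly 0–35% over ρ = 0.3–0.9 and k = 0.7–1, slightly less with 10% or 20% loss. In large samples it cannot make precision worse. Nearly all the gain comes from V2 pain; site is worth 0.5–3% of the SE under an assumed site difference in change of 0.2–0.5 SD.

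Without such a score the V2 gain disappears, and the interpretation of V3−V2 itself becomes the larger problem.

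**What to change.** 1. State which V2 6MWT supplies the movement-pain score, and that it is recorded before allocation is disclosed and before TENS starts. Reconcile this with the Order of Testing table, where only the later V2 walk carries the rating label, and with the Randomization row, which does not place disclosure within the visit.
2. If that score exists, pre-specify as primary a constrained longitudinal model: common V2 mean, time, treatment × time without a treatment main effect, site, site × time, and an unstructured 2×2 covariance. Rule out a random intercept or compound symmetry. Keep the same pairwise contrasts, the Bonferroni adjustment and all randomised participants. ANCOVA of V3 on V2, treatment and site is a near-equivalent; it drops participants without V3, but gave the same contrast in simulation when only V3 was missing.
3. If no such score exists, do not constrain or adjust for V2. Add only site and site × time, and do not describe V3−V2 change as a clean one-month effect.

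The cost is SAP text, model code including the covariance statement, and a few degrees of freedom out of about 260. No new data are needed if the pre-TENS score is already recorded, which must be confirmed first.

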Objectives	
Aim #1: The primary aim of the study is to test the effectiveness of repeated TENS use on movement-related pain in people with fibromyalgia with random assignment to three treatments: standard care, placebo TENS and active
 
Aim #2: A secondary aim will test if pain reduction by TENS results in a concomitant decrease in fatigue and fear of movement, and an increase in function and quality of life. Outcome measures will include physical function by directly assessing daily activity with an accelerometer, as well as performing specific functional tasks
 
Aim #3: To determine if active TENS alters pain processing in women with fibromyalgia and if improvement in clinical symptoms correlates with normalization of pain processing physiology. We will evaluate change in these physiologic parameters in responders versus non-responders as assessed clinically.
 
Aim #4: To determine if PROMIS is a useful instrument for assessing outcome for fibromyalgia by comparing to the revised version of the fibromyalgia impact questionnaire (FIQ-R).

Study Design	This is a phase II randomized, double-blind, placebo controlled multi-center clinical trial. The initial phase of the study will randomly allocate subjects to receive active TENS, placebo TENS or standard care (No TENS). After participating in the 1 month random assignment, all subjects will receive active TENS for 1 month. The subjects will make 4 visits to the clinic.

Subject Population	Females with fibromyalgia.
Inclusion Criteria	
 • Participants will be 18 to 70 years of age • Women may participate in the study • Diagnosis of Fibromyalgia by 1990 ACR criteria • History of cervical or lumbar pain with fibromyalgia (this is expected in all patients since axial pain is required for diagnosis) • Current stable treatment regimen for the last 4 weeks and projected stable treatment regimen for the next 2 months. • English speaking

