	FTSTS	V2 V3 V4	Function; Measure of leg strength	ICC 1 >0.95	r=0.59-0.88 LBP r=0.46-0.76 Control	^{65, 66}

	FR	V2 V3 V4	Function; Measure of balance	r=0.95	r=0.7	^{27, 67}
	Actigraph: Actisleep+	Week Before V2 V3 V4	Function: Activity and Sleep Accelerometer worn on wrist	NA	NA	NA
Quantitative Sensory Testing	PPT	V2 V3 V4	Deep mechanical hyperalgesia; Pressure Pain Thresholds	r=0.79-0.94 ICC = 0.85- 0.99 Test- retest=0.70 -0.94	Significant differences between healthy and RA subjects (p<0.05)	⁶⁸⁻⁷²
	CPM (DNIC)	V2 V3 V4	Central Inhibition	Face validity as the same test in animals activates descending inhibitory pathways		

*Table 3:
List of
equipment,
form per
test and
measure*

Order of Testing FAST June 2014

Order of Testing FAST June 2014							
Key:							
Blue= Assessor	Black= Subject	Red= TENS Allocator					
Session 1	Session 2		Session 3		Session 4		
Pre-consent Eligibility Screen	NRS Rest - Pain,Fatigue		NRS Rest - Pain,Fatigue		NRS Rest - Pain,Fatigue		
Reimbursement Form	FIQR		FIQR		FIQR		
Consent	Medication Log		Medication Log		Medication Log		
Confirmation of Consent	Eligibility		Adverse Event Screen		Adverse Event Screen		
Adverse Event Screen	Adverse Event Screen	Download Actigraph Data	Questionnaires (4-5) 1990 & 2010 ACR	Download Actigraph Data	Questionnaires (4-5) 1990 & 2010 ACR	Download Actigraph Data	
Medication Log	Questionnaires (4-5)		6MWT	Download/Record TENS Data	6MWT	Download/Record TENS Data	
Health History	6MWT		FTSTS		FTSTS		
NRS Rest - Pain,Fatigue	FTSTS		FR		FR		
FIQR	FR		PPT		PPT		
Height, Weight	PPT		TENS Treatment 1	5 min TENS Check	TENS	5 min TENS Check	
1990 FM ACR	TENS	5 min TENS Check	Questionnaires during TENS(4-5)		Questionnaires during TENS(4-5)		
2010 FM ACR	Questionnaires during TENS(4-5)		NRS Rest - Pain,Fatigue		NRS Rest - Pain,Fatigue		
Eligibility/Review	NRS Rest - Pain,Fatigue		PPT		PPT		
TENS Tolerance Test	PPT		6MWT (NRS Mvmt Pain, Fatigue, BORG)		6MWT (NRS Mvmt Pain, Fatigue, BORG)		
Actigraph	6MWT (NRS Mvmt Pain, Fatigue, BORG)		FTSTS (NRS Mvmt Pain, Fatigue)		FTSTS (NRS Mvmt Pain, Fatigue)		
Adverse Event Screen	FTSTS (NRS Mvmt Pain, Fatigue)		FR		FR		
Blood Draw	FR		CPM		CPM		
	CPM		Blinding question		GIC	TENS off	
	TENS Home		Turn off TENS		Survey		
	Actigraph Home		GIC		Survey		
	AES		Blinding question				
	Record and Clear Data		Debriefing (Active may be done)				
			Record/Clear Data				
			TENS Treatment 2	5 min TENS Check			
			NRS Rest - Pain,Fatigue				
			PPT				

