Aim #1	V3-V2	Pain NRS with movement (6MWT and FTSTS) for the treatment groups: active TENS, placebo TENS or standard care	
 • Linear mixed model analysis (LMM) for repeated measures with treatment group, time (V3-V2) and treatment group*time interaction as fixed effects. • Post-hoc pair wise comparison of mean change between all three treatment groups • p-values adjusted using Bonferroni method to account for the number of tests • Potential confounders include BMI, age, race, ethnicity, educational attainment, marital status, TENS dose/intensity, change in opioid status, medication intake, rescue medications; If there are differences between potential confounders, we will include covariates
Aim #1 Intention to Treat (ITT)	V3-V2	Pain NRS with movement (6MWT and FTSTS) for the treatment groups: active TENS, placebo TENS or standard care	
 • Intention to treat (ITT) analyses using all available data for all randomized participants will be used • If there are missing data, missing at random (MAR) LMM will be used. Sensitivity analysis will be performed using pattern mixture models since data cannot be determined if it is MAR or missing not at random (MNAR). Multiple imputation will be used for sensitivity analysis by imputing from a non-random pattern mixture model • Modified ITT (mITT) will be conducted to account for subjects who did not achieve adequate dose (based on previous work, 5% of subjects randomized to active TENS

			are expected to not achieve adequate dose). This will be limited to those who achieved at least one adequate intensity dose ^{73, 74} .
Aim #2	V3-V2	Primary: Fear of movement scores. Secondary: changes in function, fatigue, resting pain, use of rescue medications, accelerometry and quality of life questionnaires.	
 • Comparison between the randomized groups will be performed as described in Aim #1. • Additional analysis using the change in fatigue, fear of movement, function, resting pain measures and quality of life as dependent variable in linear regression models, associations between these outcomes and changes in pain values will be investigated.

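### The secondary covariate-adjusted comparison of the randomised arms lists post-randomisation variables as potential confounders and does not say how covariates enter the model

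*Combined protocol and SAP*

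**What the plan says.** The primary Aim #1 model (Study Synopsis, Statistical Methods Aim #1 - #4) has group, time (Visits 2 and 3) and group-by-time, with no covariates. The group-by-time term carries the comparison of mean change.

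If adjusted analyses prove necessary, "a secondary comparison of the change in endpoints for the three groups will be made by expanding the linear mixed model to include covariates". The candidates mix baseline characteristics (age, race, ethnicity, education, marital status) with "TENS dose/intensity, change in opioid status, medication intake and use of rescue medications". The Aim #1 row of the Data Analysis Plan table repeats the list, adds BMI and gives the trigger: "If there are differences between potential confounders, we will include covariates". It names no test or threshold.

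Other sections fix the timing:

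- **Randomisation:** "Patients will be randomly allocated on the second visit after a re-assessment of eligibility".
- **Rescue analgesic use** is a secondary endpoint of Aim #2, compared between arms by the Aim #1 methods.
- **TENS:** the exclusion criteria include "TENS use in the last 5 years". The Order of Testing table shows "Download/Record TENS Data" at Sessions 3 and 4. The only TENS measure before randomisation is the Session 1 "TENS Tolerance Test".
- **Medication:** entry requires "Current stable treatment regimen for the last 4 weeks and projected stable treatment regimen for the next 2 months".

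**The concern.** A variable that treatment can change cannot confound a comparison of randomised arms. It is a mediator, an outcome, or part of the treatment. Rescue use is the clearest case, since the plan lists it as a confounder in Aim #1 and as a between-arm outcome in Aim #2. TENS dose in use is part of the intervention and does not exist in standard care. A change in opioid status after a stable entry regimen is also post-randomisation, but should be uncommon. Medication intake has no stated timing and could be a baseline value.

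The trigger adds to the problem. Selecting covariates because they differ between arms favours those that treatment has changed.

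At stake is how the adjusted result is read. If it departs from the primary result, a reader could not tell whether the gap reflects chance baseline imbalance or adjustment for a consequence of treatment. Because Aim #2 comparisons follow the Aim #1 methods, the list carries over to them.

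**Working it through.** The plan states no figure for this analysis, so there is none to reproduce. From the documents: 88 per arm (3 × 88 = 264), two visits, Bonferroni over three pairwise tests (0.05/3). All other inputs below are assumptions.

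**1. Form of entry.** With complete data, group-by-time is the between-arm difference in mean of (Visit 3 − Visit 2). A covariate that is constant over time and entered as a main effect adds the same amount at both visits and cancels in the difference. In one fitted mixed model for active versus placebo the estimates were:

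- unadjusted: −1.172
- time-constant main effect: −1.172
- covariate-by-time: −0.928
- time-varying: −0.973

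**2. Rescue-by-time, active versus standard care.** Pain at Visit 3 = 6 + b + a·active + 1.2·U3 + e + g·R, and the same at Visit 2 without treatment. SD(b) = 1.4, SD(e) = 0.8, a = −1. R = 1 if L·U3 − s·active + N(0,1) > 0.3. L is how strongly rescue use tracks flares, s is how far active TENS lowers it, and g is the effect of rescue on pain. With g = 0 the SD of change is √[2(1.2² + 0.8²)] = √4.16 ≈ 2.04. The arms differ by 11 to 25 percentage points in rescue use. Mean estimates, unadjusted → adjusted, 2,000 trials each:

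| L, s | g = 0 | g = −0.5 | g = −1 |
|---|---|---|---|
| 0.4, 0.4 | −1.00 → −0.90 | −0.95 → −0.92 | −0.86 → −0.89 |
| 0.4, 0.8 | −1.00 → −0.83 | −0.89 → −0.83 | −0.76 → −0.82 |
| 0.8, 0.4 | −1.00 → −0.86 | −0.94 → −0.85 | −0.88 → −0.86 |
| 0.8, 0.8 | −1.00 → −0.74 | −0.89 → −0.73 | −0.78 → −0.73 |

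Shifts run from 26% smaller (0.26/1.00) to 8% larger (0.06/0.76); the smallest is about 3%. In these settings the adjusted figure generally matches neither the total effect (unadjusted column) nor the direct effect (−1.0). When rescue use does not track flares (L = 0), adjustment recovers the direct effect, 0 to 32% larger than the total, which is a different question.

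**3. Null case** (a = 0, g = 0, rescue use lower on active). In the strongest setting (L = s = 0.8) the adjusted estimate is +0.25 and rejection at 0.05/3 is about 6%, against 1% to 2% unadjusted. In the mildest (L = s = 0.4) the estimate is about +0.1 and rejection 2% to 3%, which is little change.

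**4. Change in opioid status by time.** The shift is at most 3% if 2% of standard care change, 6% at 5%, and 11% at 10%.

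**5. Dose-by-time.** Let CV be the coefficient of variation of dose among users. The SE ratio for active versus standard care is:

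- only active use counts: √(1 + 1/(2CV²)) = 3.67, 2.56, 1.73 at CV 0.2, 0.3, 0.5
- placebo use counts too: √(1 + 1/(4CV²)) = 2.69, 1.94, 1.41

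For active versus placebo, the ratio is 1.00 if placebo use counts, because mean dose is then the same in both arms. It is about 1.7 to 3.7 if only active use counts. If dose is coded missing for standard care, complete-case fitting drops that arm and leaves 2 × 88 = 176 of 264.

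**6. Fix.** One pre-randomisation covariate (Visit 2 rescue use) with its time term left the estimate within 0.5% of unadjusted, with an SE ratio of 0.96 to 1.00. With 16 uninformative covariate terms (an assumed number) the ratio was 1.03. The full recommended set has not been simulated.

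**The case against.** The strongest objection is low stakes. The analysis is secondary, conditional, and drawn from a list of candidates, and the plan expects randomisation to lessen the need for it. That stands: no primary estimate, test or sample size changes.

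The large shifts also need favourable inputs. The 26% figure and the null inflation both assume that rescue analgesics do not affect pain. Where rescue lowers pain by 1 point and tracks flares, the shift is only about 0.03 to 0.07 points. Change in opioid status should be rare under the stability criteria. These points stand and limit the weight of the numbers, but they do not make a post-randomisation variable a confounder.

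TENS intensity might mean the Session 1 tolerance value. Nothing says so, and the Aim #1 text uses adequate intensity dose for what randomised patients achieve.

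A reader might infer that dose adjustment spoils the blinded comparison. The documents do not support that in general: the Study Synopsis lists TENS parameters for active and placebo units together, and if placebo use counts as dose, active versus placebo loses no precision.

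A reader might also infer that the plan contradicts its own rule in Aim #3. It does not. The pre-intervention restriction there concerns predicting responders, and the Aim #3 covariates are justified because responder status is not randomised. Neither is a rule for adjusting comparisons between arms.

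**Conclusion.** The concern holds for the conditional adjusted comparison in Aim #1 and for the Aim #2 comparisons that follow its methods. Rescue use and TENS dose in use are the main problems; change in opioid status is a lesser one. Depending on a form of entry that the plan leaves open, adjustment either does nothing to the comparison of change or replaces the randomised effect with another quantity.

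The size rests wholly on assumed inputs and should not be read as the bias expected in this trial. A different set of assumptions (active TENS lowering rescue use by 1 SD, with or without an unmeasured common cause of rescue use and pain) moved a true active-versus-placebo effect of −1.0 to anywhere between −1.00 and +0.10.

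It would be tempting to conclude that the primary result is compromised. The documents do not support that, because the primary intention-to-treat model has no covariates. This should be corrected, but it does not threaten the main inference.

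**What to change.** Restrict adjusted comparisons of randomised arms in Aims #1 and #2 to prespecified covariates fixed before randomisation: for example site, age, race, ethnicity, education, marital status, BMI, and opioid and medication use from the Visit 1 and Visit 2 medication logs. Enter each with a covariate-by-time term. Replacing the trigger based on observed differences with a fixed set is good practice but partly preference; timing and form of entry are the essential changes.

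Remove TENS dose/intensity in use, change in opioid status, rescue use and on-study medication intake from those models. Keep rescue use as an Aim #2 outcome. Keep dose-response within active TENS as a labelled exploratory, non-randomised analysis. If intensity means the Session 1 tolerance value, say so; it may then stay as a baseline covariate.

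The cost is SAP wording, loss of the between-arm dose-adjusted estimate, and possibly a few percent in standard error if many uninformative covariates are entered.
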